
Date: February 23, 2024

Protocol V11

contributes to lower synthesis and expression of MHC-I. On the other hand, failure to increase synthesis rate of MHC-I under these conditions, will suggest a defect that is specific to the MHC-I translation. Our studies will, therefore, pinpoint specific biological defects that sustain unfavorable muscle fiber phenotype in humans with obesity, and which is key in any effort to address metabolic abnormalities (i.e., impaired muscle glucose uptake) originating from an unfavorable muscle fiber phenotype in these humans.

Specific Aims

Aim 1. To determine the turnover rate of MHC isoforms and overall muscle protein in skeletal muscle of subjects with obesity and lean controls in the basal state. We hypothesize lower synthesis rate of MHC-I (due at least in part to lower MHC-I mRNA) along with lower overall muscle protein synthesis in skeletal muscle of humans with obesity, and concomitant with lower formation of the eukaryotic initiation factor 4F (eIF4F) in muscle (key protein-complex signaling overall translation/synthesis). We hypothesize that muscle MHC-IIx synthesis is not reduced in obesity, and despite lower eIF4F complex formation in muscle, because the presence of higher MHC-IIx mRNA expression in muscle of humans with obesity.

Aim 2. To determine stimulation of the turnover rate of MHC isoforms in skeletal muscle of subjects with obesity and lean controls by plasma amino acids and with and without prior exercise. We hypothesize that increasing the plasma amino acid concentrations alone increases the basal rate of synthesis across all MHC isoforms in both lean and obese subjects, revealing a response largely dependent upon their respective mRNA expressions. This is because plasma amino acids enhance the overall protein translation in muscle (i.e., increase muscle eIF4F complex formation). We hypothesize that acute aerobic exercise alone does not increase the basal-state MHC-I synthesis rate in either lean or obese subjects, and despite greater increase in MHC-I mRNA expression in muscle of subjects with obesity. Thus, we also hypothesize that coupling the plasma amino acid stimulus to the exercise stimulus will increase the synthesis rate of the MHC-I in the subjects with obesity, revealing that impaired overall muscle protein translation is also responsible (and in addition to lower basal-state MHC-I mRNA, Aim#1) for lower MHC-I expression in muscle of humans with obesity.

Approach

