To test our hypotheses, we propose to study both subjects with obesity and lean controls. Each subject will take part in a single infusion trial. The infusion trial will consist of a Basal study period and an Experimental study period (**Fig. 1**). The Experimental study period will include either an acute session of aerobic exercise following by amino acid infusion (EX+AA trial) or amino acid infusion alone (AA trial). The exercise stimulus is designed to primarily target the MHC-I mRNA expression and synthesis of MHC-I in muscle ((our preliminary evidence for MHC-I mRNA and (63, 64, 82)). The amino acid infusion is designed to specifically upregulate the overall protein translation in muscle (65, 66), and we have shown to increase global (i.e., mixed muscle) protein synthesis in both lean humans as well as humans with obesity (8). Our preliminary evidence does not show increase in the synthesis rates of either mixed-muscle, mitochondrial (data not shown), or MHC-I protein following exercise alone. However, we propose to expand this preliminary evidence in lean humans and humans with obesity. Therefore, we will test the effects of exercise alone (EX trial) in groups of subjects that are separate from the lean and obese subject groups indicated above, and by following same experimental procedures as in the EX+AA trial but without the infusion of amino acids. We will study subjects with obesity (N=9) and lean controls (N=9) to test the hypothesis that exercise alone does not stimulate the synthesis of MHC-I, and despite increase in MHC-I mRNA expression by exercise. With the exception of the exercise session, subjects will be resting in bed for the duration of each trial.

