Our main end-points in the proposed studies are the synthesis rates of mixed-muscle protein, mixed-mitochondrial protein, as well as MHC isoforms, particularly MHC-I, whose synthesis rate we found to be lower in subjects with obesity, in our preliminary studies. These preliminary data also show that MHC-I synthesis rate does not increase in response to our experimental manipulation (i.e., exercise stimulus alone) despite an increase in MHC-I mRNA. Therefore, other main end-points are the expression of mRNA of MHC isoforms as well as the formation of the active eIF4F complex, which has key role in translation initiation in skeletal muscle, and which we found in our preliminary studies to be lower in muscle from humans with obesity. Statistical significance will be calculated using 2-way repeated measures ANOVA.

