concentrations coupled to the exercise stimulus, and another 17 will serve as controls, for a total 34 lean subjects participating in the study. Main outcome in the exercise-alone studies is the increase in MHC-I mRNA expression after aerobic exercise, and which we show to increase only in the subjects with obesity. In our preliminary studies we detected a difference of 0.94 SD for MHC-I mRNA expression between before and after exercise in subjects with obesity. A sample of 9 subjects per group will have sufficient power (80%) to detect 0.94 SD difference ($\alpha = 0.05$) in MHC-I mRNA expression. Therefore, we will study 9 lean subjects and 9 subjects with obesity in the groups that will undergo exercise-alone trial. Sample size estimates and power were calculated using paired t-tests with an overall $\alpha = 0.05$ and $\alpha = 0.0125$ for Bonferroni-adjusted multiple comparisons. We propose to enroll 2 more subjects/group for the amino acid infusion and exercise+amino acid infusion studies (to the overall 34 subjects per group indicated above for those studies), to account for unsuccessful experiments and/or increase the statistical power in pair-wise comparisons with the lowest effect size, for a total of 36 lean subjects and 36 subjects with obesity for the studies related to the amino acid infusion and exercise+amino acid infusion. Therefore, we will enroll a total of 90 subjects.

Protection of Human Subjects

Risks to Human Subjects

Human Subjects Involvement, Characteristics, and Design

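### Exercise alone is hypothesised not to raise MHC-I synthesis, but the plan has only a significance test at 9 per group, so a non-significant result could not support that absence

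*Combined protocol and SAP*

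**What the plan says.** Under Specific Aims, Aim 2 states the absence for each group: "We hypothesize that acute aerobic exercise alone does not increase the basal-state MHC-I synthesis rate in either lean or obese subjects". The Experiments section sets up separate exercise-alone groups of 9 lean subjects and 9 subjects with obesity "to test the hypothesis that exercise alone does not stimulate the synthesis of MHC-I, and despite increase in MHC-I mRNA expression by exercise".

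Statistical Design and Power lists MHC-I synthesis among the main end-points of the studies and gives one analysis rule: "Statistical significance will be calculated using 2-way repeated measures ANOVA". It gives no margin, equivalence test or confidence-interval criterion. For the exercise-alone groups it names a different outcome, "Main outcome in the exercise-alone studies is the increase in MHC-I mRNA expression after aerobic exercise", and sizes them on that: "A sample of 9 subjects per group will have sufficient power (80%) to detect 0.94 SD difference". No power or precision is given for MHC-I synthesis after exercise alone. The two extra subjects per group are for the amino acid and exercise-plus-amino-acid studies only.

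Aim 1 contains a second hypothesis of absence: "We hypothesize that muscle MHC-IIx synthesis is not reduced in obesity".

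**The concern.** A test of difference can support a rise but cannot by itself support the absence of one. If a non-significant change is read as confirming the hypothesis, imprecision works in the hypothesis's favour: fewer subjects or a noisier assay make it easier to confirm. The Significance section interprets unchanged MHC-I synthesis alongside raised MHC-I mRNA as translational resistance, and the exercise-alone groups are there to extend that evidence. A rise that was real but missed could therefore be published as a biological finding.

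**Working it through.** **Inputs.** From Statistical Design and Power: 9 per group; 0.94 SD for mRNA; 1.15 SD as the assumed MHC-I synthesis response to exercise plus amino acids; paired t-tests; alpha 0.05 overall and 0.0125 for Bonferroni-adjusted comparisons. Effects are taken as SDs of the within-subject change, because the plan names paired tests. Two-sided testing is assumed, because sidedness is not stated. The documents give no expected rise in synthesis after exercise alone, so 0.5 and 0.75 SD are assumptions. The 1.15 SD value is the plan's only benchmark for a rise in MHC-I synthesis.

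**The plan's own figure.** By the normal approximation, power = Φ(d√n − 1.96) = Φ(0.94 × 3 − 1.96) = Φ(0.86) = 80.5%. The required n is ((1.96 + 0.842)/0.94)² = 8.9, so 9. The stated 80% reproduces. The exact two-sided paired t-test gives 69.6%.

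**Chance of missing a rise in synthesis, n = 9 in one group.** Missed = 1 − P(|T| > c), where T is noncentral t with 8 df and noncentrality d√9 = 3d. The critical value c is 2.306 at alpha 0.05 and 3.206 at alpha 0.0125.

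| True rise (SD of change) | Non-significant, alpha 0.05 | Non-significant, alpha 0.0125 |
|---|---|---|
| 0.5 (assumed) | 74% | 90% |
| 0.75 (assumed) | 49% | 75% |
| 1.15 (plan's EX+AA value) | 15% | 39% |
| 1.5 (assumed) | 2.5% | 14% |

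**Precision.** The 95% half-width is t(0.975, 8)/√9 = 2.306/3 = 0.77 SD. An observed change of exactly zero would still be compatible with a rise of about three-quarters of an SD.

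**What a confidence-limit rule can deliver at n = 9.** The chance that a one-sided 95% upper limit falls below margin m is P(T > 1.860), where T has 8 df and noncentrality 3(m − true change).
- m = 1.15 SD: 93% if the true change is zero. However, a true 0.5 SD rise would still be labelled no relevant increase about 55% of the time, and a 0.75 SD rise 29%. This margin is too lax.
- m = 0.575 SD (half of 1.15, for illustration): 47% if the true change is zero. An 80% chance needs 21 per group.

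**MHC-IIx.** The Experiments section gives every subject a Basal period and the d₁₀-leucine tracer, so each body-size group can contribute 36 + 9 = 45 subjects. For an assumed 0.75 SD reduction, a two-sided two-sample t-test at alpha 0.05 (noncentrality 0.75√(45/2) = 3.56, 88 df) misses 6%. At 17 per group it misses 44%.

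**The case against.** The strongest reply is that the documents nowhere say non-significance will be taken as proof of absence, and that mRNA is the declared main outcome of the exercise-alone trial, so sizing on mRNA is consistent. Both statements are true. They do not supply a rule for a hypothesis that the Experiments section says these groups will test.

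The frequency of a missed rise depends on effects that the documents do not give. At the plan's own 1.15 SD and alpha 0.05 it is 15%. Pooling lean and obese subjects (n = 18) cuts the miss rate for 0.75 SD to 15% if the rise is equal in both. That helps, but Aim 2 states the hypothesis for each group.

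Three stronger readings are tempting and not supported:
- *That an mRNA rise confined to obesity will be inferred by comparing a significant result in one group with a non-significant one in the other.* The phrase "and which we show to increase only in the subjects with obesity" describes preliminary data, and a 2-way repeated measures ANOVA ordinarily supplies the group-by-period interaction.
- *That the inference from a failed exercise-plus-amino-acid response has the same weakness.* The plan does say that "failure to increase synthesis rate of MHC-I under these conditions, will suggest a defect that is specific to the MHC-I translation", but 17 subjects miss the assumed 1.15 SD under 1% of the time at alpha 0.05 and about 4% at 0.0125.
- *That the MHC-IIx comparison is badly underpowered.* That holds at 17 per group, not with all 45 per group.

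Nor does the whole mechanistic argument rest on the exercise-alone null. The plan also relies on positive effects: lower basal eIF4F formation in obesity, and a rise in MHC-I synthesis with exercise plus amino acids.

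**Conclusion.** The point holds for MHC-I synthesis after exercise alone. The plan tests a hypothesis of no increase in each of two groups of 9, with only a significance test and no precision target for that outcome. Rises below about 1 SD of the within-subject change would often be non-significant at alpha 0.05; at alpha 0.0125 that extends to about 1.15 SD. Rises of 1.5 SD or more would rarely be missed at alpha 0.05. These figures assume two-sided paired t-tests, effects expressed in SDs of the change, and no lost experiments.

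A reader might infer that the plan commits itself to accepting p > 0.05 as proof. It does not say so; the gap is that it offers no other criterion. For MHC-IIx the same gap in the rule exists, but the design can give reasonable precision if all Basal data are used. This should be corrected before analysis; it does not invalidate the trial.

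**What to change.** Add to Statistical Design and Power:
- Absence of an effect will not be inferred from p > 0.05.
- For the exercise-alone trial, the change in MHC-I synthesis from Basal will be reported with its confidence interval, separately for lean subjects and subjects with obesity.
- No relevant increase will be concluded in a group only if the upper confidence limit lies below a margin set before analysis. The confidence level is to be stated, for example a one-sided 95% limit. The sponsor should state the margin in synthesis-rate units and justify it as negligible, so it must be clearly smaller than the 1.15 SD assumed for exercise plus amino acids. The documents give no SD in those units, so the sponsor must supply it. Otherwise the result is reported as inconclusive.
- For MHC-IIx, the obese-minus-lean difference in Basal synthesis will be reported with its confidence interval, using all 45 subjects per group.

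This needs no new subjects, samples or procedures. The cost is in the claim: with 9 per group a strict margin will often end as inconclusive (47% power at 0.575 SD with a one-sided 95% limit, even if exercise truly has no effect). The exercise-alone conclusion should be worded no more strongly than its interval allows.

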Subjects will arrive at the CSIU at ~ 6:30 AM, after an overnight (10-hour) fast. An intravenous (IV) line will be inserted into an antecubital vein for infusions, whereas a second one will be inserted in a retrograde fashion into a vein of the opposite hand for arterialized blood sampling, and where the hand will be placed into a heated box (i.e., heated-hand technique (83)). Prior to initiation of any infusions, blood samples will be obtained for the measurement of background isotopic enrichment and fasting blood chemistry parameters. At ~ 7:30 AM (time 0; **Fig. 1**) infusions of L-[2,3,3,4,5,5,6,6,6-²H₁₀]leucine (d₁₀-leucine; prime: 9.0 umol·kg FFM⁻¹; rate: 0.15 umol·kg FFM⁻¹·min⁻¹), L-[ring-¹³C₆]phenylalanine and L-[¹⁵N]phenylalanine (for both, prime: 3.0 umol·kg FFM⁻¹; rate 0.06 umol·kg FFM⁻¹·min⁻¹) (Cambridge Isotope Laboratories, Inc., Andover, MA) will be started to enrich the muscle pool of intracellular amino acids with amino acid tracers for the determination of the rates of synthesis and breakdown of muscle proteins. The infusions of d₁₀-leucine and L-[ring-¹³C₆] phenylalanine will be continued for the duration of the study, whereas that of the [¹⁵N]phenylalanine tracer will be stopped 3.5 hrs after its initiation, and as shown in **Fig. 1**, for the determination of the fractional breakdown rate of mixed-muscle protein in the Basal state. Alternatively, the stable isotopes of leucine and phenylalanine may be ingested instead of infused. In case of ingestion, the stable isotopes of these amino acids will be provided as small boluses dissolved in water (~10-20ml) and ingested every 10-15 minutes, and at a rate similar to that indicated for infusion. Rate of mixed-muscle protein synthesis in the Basal state will be simultaneously determined with that of mixed-muscle protein breakdown from the L-[ring-¹³C₆] phenylalanine tracer incorporation into mixed-muscle protein. It is noted that combined fractional synthesis and breakdown of mixed-muscle protein will be evaluated only in a subset of subjects, and because of that, the two phenylalanine tracers, which are used together to simultaneously determine synthesis and breakdown of mixed-muscle protein, will not be administered in all subjects. . The d₁₀-leucine tracer will be used for the determination of the rate of synthesis of the MHC isoforms as well as mixed-muscle protein, and administered in all subjects. For the measurements of protein turnover in the Basal state biopsies of vastus lateralis muscle will be collected at 2 (1st biopsy) and 4.5 (2nd biopsy) hours after the start of the amino acid tracer infusions. Blood samples specifically for the determination of mixed-muscle protein breakdown will be collected similar to what has been previously described (84-86). Following data collection in the Basal state, the Experimental Study Period will be initiated immediately after the 2nd biopsy. During the Experimental Study Period in the EX+AA trial, subjects will first perform cycle-ergometer exercise at 65% VO_{2peak} for 45 min. Following exercise, subjects will immediately receive infusion of an amino acid solution (prime, 82 mg·kg FFM⁻¹; infusion rate, 4 mg·kg FFM⁻¹·min⁻¹; 15% Clinisol; Baxter Healthcare Corporation, Deerfield, IL) for the remainder of the study trial. This is a balanced mixture of amino acids. It contains both essential (all essentials) and non-essential amino acids (for a total of 17 amino acids) and increases these amino acids in plasma. The amino acid mixture was chosen because we have previously shown to upregulate protein synthesis in skeletal muscle (8, 87). Increase in the essential amino acids, and specifically leucine, is important to drive upregulation of these processes in muscle (88-90), with the non-essential amino acids supporting the overall protein synthesis machinery. Therefore, this amino acid mixture, which contains sufficient amount of leucine, was chosen specifically based on our own evidence that it induces stimulation of overall/mixed-muscle protein synthesis in both lean humans and humans with obesity (8, 87). Infusion, when compared to ingestion, ensures comparable plasma amino acid concentrations between lean subjects and subjects with obesity (i.e., avoids differences in plasma amino acids as result of differences in gut amino acid absorption), and prevents amino acid-dose response effects seen in heterogenous groups of subjects with orally ingested amino acids (91, 92). In the AA trial, subjects will receive the same infusion of amino acids, but no exercise will be performed prior to the amino acid infusion. We have shown that the proposed dose of amino acids alone is sufficient to stimulate

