
Calculations. Fractional synthetic rate of mixed-muscle and mixed-mitochondrial proteins will be determined using the precursor-product method based on the phenylalanine amino acid enrichments measured in the blood amino acid and muscle protein pools, following procedures we have recently described (8, 9, 87). Fractional breakdown rate of mixed-muscle protein will be determined directly in muscle (i.e., *not by using the arterio-venous technique*) following procedures previously described (84-86). We have previously validated a method to determine application of the d₁₀-leucine tracer to measure fractional synthetic rate of protein in muscle (87). Fractional synthetic rate of individual MHC isoforms will be calculated from d₉-leucine enrichments measured in the blood and the muscle MHC isoforms (i.e., MHC-I, MHC-IIa, MHC-IIx). We have previously developed (112), and successfully applied (9) a methodology to measure the fractional synthesis rate of an individual protein in skeletal muscle, and we will use similar procedures with respect to the fractional synthesis rates of the MHC isoforms. Fractional breakdown rate of the individuals MHC isoforms will be calculated from the measurement of the fractional synthesis rate of each MHC isoform in combination with the fractional change in that MHC isoform's concentration over a given time period, and as previously described (114, 115).

Immunoprecipitation and immunoblotting. We will follow procedures similar to those we and [name] have used in the past (7, 8, 116-118). With respect to the 4E-BP1·eIF4E and eIF4G·eIF4E complexes (which are key measurements in this proposal), these will be quantified after eIF4E is immunoprecipitated (IP) from aliquots of supernatants using an anti-eIF4E monoclonal antibody (generated in [name] laboratory). Antibodies not generated in [name] laboratory will be commercially obtained and authenticated in [name] laboratory. We will also measure in the same muscle samples MOTS-c (mitochondrial open reading frame of the twelve S rRNA type-c). MOTS-c will be measured in muscle samples as well as plasma samples.

Date: February 23, 2024

Protocol V11

MOTS-c is a novel mitochondrial peptide in muscle, and which is also released into the circulation in association with physical activity/exercise. Recent evidence shows that it regulates metabolic processes in muscle that can be linked to protein synthesis.

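### Mixed-muscle synthesis has two conflicting tracer definitions, and mixed-mitochondrial synthesis is calculated only from tracers given to a subset of unstated size

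*Combined protocol and SAP*

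**What the plan says.** Statistical Design and Power opens: "Our main end-points in the proposed studies are the synthesis rates of mixed-muscle protein, mixed-mitochondrial protein, as well as MHC isoforms, particularly MHC-I".

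The Calculations paragraph (Analyses of Samples and Calculations) says how each rate is obtained. Mixed-muscle and mixed-mitochondrial FSR are "based on the phenylalanine amino acid enrichments measured in the blood amino acid and muscle protein pools". FSR of the MHC isoforms comes from d9-leucine enrichment. The paragraph adds that a d10-leucine method for FSR of muscle protein was validated earlier.

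The Experiments section limits who receives phenylalanine: "combined fractional synthesis and breakdown of mixed-muscle protein will be evaluated only in a subset of subjects", and therefore "the two phenylalanine tracers, which are used together to simultaneously determine synthesis and breakdown of mixed-muscle protein, will not be administered in all subjects". One sentence there takes Basal mixed-muscle synthesis from the ring-13C6 phenylalanine tracer. A later one says the d10-leucine tracer is for "determination of the rate of synthesis of the MHC isoforms as well as mixed-muscle protein, and administered in all subjects". Mitochondrial protein is not in that list.

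The paragraph on stable isotope enrichment states that mixed-muscle protein, mixed-mitochondrial protein and blood are all assayed for d9-leucine as well as for both phenylalanine labels.

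Statistical Design and Power claims more than 95% power with 17 per group for Basal lean-obese differences of 2.0 SD in mixed-muscle synthesis and 3.5 SD in breakdown.

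**The concern.** Followed to the letter, the Calculations paragraph cannot produce either FSR in a subject who received no phenylalanine tracer. The size of that group is unknown, as is its spread over lean and obese subjects and over the AA, EX+AA and EX trials.

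The two end-points stand differently. Mixed-muscle synthesis has two definitions, one for the subset and one for everyone, and the plan does not say which is the main one. Mixed-mitochondrial synthesis has one definition, and it works only in the subset.

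Two things are at stake. First, the tracer could be chosen for each end-point after the results are seen. Second, phenylalanine values from some subjects could be pooled with leucine values from others. If the subset were uneven across groups, any systematic offset between the tracers would enter the group contrast. The planned two-way repeated measures ANOVA has no rule for an outcome that is partly measured or measured in two ways.

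**Working it through.** **Which tracer supports which end-point**

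| End-point | Calculations paragraph | Experiments section | Assayed in the fraction |
|---|---|---|---|
| Mixed-muscle FSR | phenylalanine | ring-13C6 phenylalanine (subset) and d10-leucine (all) | both |
| Mixed-mitochondrial FSR | phenylalanine | no tracer assigned | both |
| MHC isoform FSR | d9-leucine | d10-leucine (all) | d9-leucine (on peptides) |
| Mixed-muscle breakdown | method cited, tracer not named | phenylalanine pair (subset) | not applicable |

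Only the MHC row is consistent and covers every subject. In the first two rows the leucine measurement exists in all subjects, but the stated calculation does not use it. Breakdown has no leucine alternative and is a subset measurement by design.

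**Power**

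Inputs from Statistical Design and Power: 17 per group; 2.0 SD (synthesis) and 3.5 SD (breakdown); alpha 0.05, or 0.0125 after Bonferroni adjustment. Sidedness is not stated, so two-sided tests are assumed. The section says power was computed with paired t-tests, but lean versus obese is a comparison of independent groups, so a two-sample t-test is used here.

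With n per group and standardised difference d, power is the probability that a noncentral t variable with 2n − 2 degrees of freedom and noncentrality d × √(n/2) exceeds the critical value in absolute size.

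The plan's figure first: n = 17, d = 2.0 gives noncentrality 2.0 × √8.5 = 5.83 on 32 degrees of freedom. Power is 99.99% at alpha 0.05 and 99.9% at 0.0125. The stated figure of more than 95% is reproduced. For d = 3.5 the noncentrality is 3.5 × √8.5 = 10.2, and power is essentially 100%.

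The documents give no subset size, so the sizes below are assumptions. The 2.0 SD columns matter only if mixed-muscle synthesis were confined to the subset.

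| n per group | 2.0 SD, alpha 0.05 | 2.0 SD, alpha 0.0125 | 3.5 SD, alpha 0.05 | 3.5 SD, alpha 0.0125 |
|---|---|---|---|---|
| 3 | 46% | 19% | 89% | 57% |
| 4 | 66% | 35% | 98% | 87% |
| 5 | 79% | 52% | 99.8% | 97% |
| 6 | 88% | 66% | >99.9% | 99.4% |
| 7 | 93% | 77% | >99.9% | 99.9% |
| 8 | 96% | 85% | >99.9% | >99.9% |
| 10 | 99% | 94% | >99.9% | >99.9% |
| 11 | 99.4% | 96.5% | >99.9% | >99.9% |

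More than 95% power at 2.0 SD therefore needs about 8 per group at alpha 0.05, or about 11 at 0.0125. At 3.5 SD it needs 4 per group at 0.05, or 5 at 0.0125.

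For mixed-mitochondrial synthesis no power can be computed, because the plan gives no effect size for it.

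**The case against.** The strongest reply is that nothing need be lost. The Experiments section already gives leucine to all subjects for mixed-muscle synthesis. Leucine enrichment is assayed in the mitochondrial fraction and in blood, and the leucine method is described as validated. What is confined to the subset is a deliberate sub-study of combined synthesis and breakdown. Basal data exist in every trial, so up to 36 + 9 = 45 subjects per BMI group could contribute. The subset would have to fall below 8 of those 45 to break the 2.0 SD claim at alpha 0.05, and nothing in the plan suggests that.

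Most of this stands, and it rules out several stronger readings:

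- A reader might infer that both end-points will be missing outside the subset. For mixed-muscle synthesis the documents say otherwise. For mixed-mitochondrial synthesis the measurement is planned; what is absent is a calculation that uses it.
- A reader might infer that the study is underpowered, perhaps by applying the plan's 1.1 SD or 1.15 SD to the subset. Those effects belong to eIF4F complex formation and to the MHC-I response, and neither depends on phenylalanine.
- A reader might divide the subset over the three trials and find very few subjects in each. The 2.0 and 3.5 SD differences are Basal lean-obese contrasts, and Basal data can be pooled over trials.
- A reader might infer that tracer is confounded with group. No text says that subset membership differs by BMI group or trial; the plan merely does nothing to prevent it.

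The reply does not remove the conflict. The one paragraph that defines the calculation names a tracer that some subjects do not receive, and no sentence applies leucine to mitochondrial synthesis.

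**Conclusion.** The point holds as a defect in end-point definition. Mixed-muscle synthesis has two conflicting tracer definitions. Mixed-mitochondrial synthesis, as written, can be calculated only in a subset of unstated size and selection. Breakdown is powered at 17 per group although the plan itself confines it to that subset.

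No stated power figure is shown to be wrong. At 17 per group the mixed-muscle claim is correct, and it would survive a subset of about 8 per group at alpha 0.05 or about 11 at 0.0125. The breakdown claim survives 4 per group at alpha 0.05. These results assume two-sided two-sample t-tests and the plan's own effect sizes. The effect on mitochondrial synthesis cannot be quantified from the documents.

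This is more than a missing detail: a stated calculation for main end-points cannot be carried out in every subject, while one that can is already supported by the planned assays. It should be settled before any synthesis rate is analysed.

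**What to change.** 1. In the Calculations paragraph, base the main analysis of mixed-muscle and mixed-mitochondrial FSR on d9-leucine enrichment in every subject, as is already done for the MHC isoforms. Bring the Experiments section into line by adding mitochondrial protein to the stated uses of leucine.
2. State that the two tracers will not be mixed within a comparison.
3. Make phenylalanine-based FSR and mixed-muscle breakdown a secondary analysis in the subset. State how the subset is chosen and its n by BMI group and by trial.
4. In Statistical Design and Power, quote breakdown power at the subset n instead of 17 per group.

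Leucine for all is not the only coherent choice, but it is the one that the administered tracers and planned assays already support in all subjects. The cost is wording only: no added procedure, sample or assay.
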